7.2. Screening and Critical Baseline Assessments

Before any study-specific procedure is performed, valid informed consent and assent as appropriate must be obtained.

Demography and medical history (including cardiovascular medical history/risk factors, T2DM history, history of other prior and concomitant medical conditions, and substance usage) will be assessed at screening (as detailed in the eCRF).

Critical baseline assessments will include: HbA_{1c}, FPG and immunogenicity.

Full details of screening and baseline assessments are provided in the Time and Events Table Section 7.1.

7.3. Efficacy

HbA_{1c} and FPG will be measured at the time points specified in the Time and Events Schedule in Section 7.1. Blood samples for HbA_{1c} and FPG should be collected before administration of study treatment.

7.4. Safety

Planned time points for all safety assessments are listed in the Time and Events Table (Section 7.1). Unscheduled visits will occur as medically necessary. Detailed procedures for obtaining each assessment are provided in the SRM.

7.4.1. Adverse Events (AE) and Serious Adverse Events (SAEs)

The definitions of an AE or SAE can be found in [Appendix 5](#).

The investigator and their designees are responsible for detecting, documenting and reporting events that meet the definition of an AE or SAE.

7.4.1.1. Time period and Frequency for collecting AE and SAE information

AEs and SAEs will be collected from the start of Study Treatment until the follow-up contact (see Section 7.4.1.3), at the timepoints specified in the Time and Events Table (Section 7.1).

Medical occurrences that begin prior to the start of study treatment but after obtaining informed consent may be recorded on the Medical History/Current Medical Conditions section of the eCRF.

Any SAEs assessed as related to study participation (e.g., protocol-mandated procedures, invasive tests, or change in existing therapy) or related to a GSK product will be recorded from the time a subject consents to participate in the study up to and including any follow-up contact.

All SAEs will be recorded and reported to GSK within 24 hours, as indicated in [Appendix 5](#).

Investigators are not obligated to actively seek AEs or SAEs in former study subjects. However, if the investigator learns of any SAE, including a death, at any time after a subject has been discharged from the study, and he/she considers the event reasonably related to the study treatment or study participation, the investigator must promptly notify GSK.

NOTE: The method of recording, evaluating and assessing causality of AEs and SAEs plus procedures for completing and transmitting SAE reports to GSK are provided in [Appendix 5](#)

7.4.1.2. Method of Detecting AEs and SAEs

Care will be taken not to introduce bias when detecting AEs and/or SAEs. Open-ended and non-leading verbal questioning of the subject is the preferred method to inquire about AE occurrence. Appropriate questions include:

“How are you feeling?”

“Have you had any (other) medical problems since your last visit/contact?”

“Have you taken any new medicines, other than those provided in this study, since your last visit/contact?”

7.4.1.3. Follow-up of AEs and SAEs

After the initial AE/SAE report, the investigator is required to proactively follow each subject at subsequent visits/contacts. All SAEs and non-serious AEs of special interest (as defined in Section 4.6.1 and Section 7.4.1.5) will be followed until resolution, until the condition stabilizes, until the event is otherwise explained, or until the subject is lost to follow-up (as defined in Section 5.5). Further information on follow-up procedures is given in [Appendix 5](#).

7.4.1.4. Cardiovascular and Death Events

For any cardiovascular events detailed in [Appendix 5](#) and all deaths, whether or not they are considered SAEs, specific Cardiovascular (CV) and Death sections of the eCRF will be required to be completed. These sections include questions regarding cardiovascular (including sudden cardiac death) and non-cardiovascular death.

The CV eCRF pages are presented as queries in response to reporting of certain CV (MedDRA) Medical Dictionary for Regulatory Activities terms. The CV information should be recorded in the specific cardiovascular section of the eCRF within one week of receipt of a CV Event data query prompting its completion.

The Death eCRF page is provided immediately after the occurrence or outcome of death is reported. Initial and follow-up reports regarding death must be completed within one week of when the death is reported.

7.4.1.5. AEs of Special Interest

In the Phase IIIa clinical development program, AEs of special interest included several areas of safety related concern for the T2DM population, particularly for a GLP-1R agonist such as albiglutide.

Specific eCRF pages will be used to capture additional details for the following AEs of special interest:

- Hypoglycemic events
- Liver events
- CV events (see Section [7.4.1.4](#))
- Injection site reactions
- Potential systemic allergic reactions
- Pancreatitis
- MTC
- Diabetic retinopathy
- Pneumonia
- Atrial fibrillation/atrial flutter

The following additional AEs of special interest will be captured in the AE eCRF pages:

- GI events
- Pancreatic cancer
- Malignant neoplasms
- Appendicitis

Subjects with drug hypersensitivity reactions that are not reasonably attributable to another cause or pancreatitis should discontinue investigational product and should not be rechallenged with albiglutide (see Section [5.5](#) for complete list of AEs of special interest requiring withdrawal).

7.4.1.6. Regulatory Reporting Requirements for SAEs

Prompt notification by the investigator to GSK or GSK designee of SAEs and non-serious AEs related to study treatment (even for non-interventional post-marketing studies) is essential so that legal obligations and ethical responsibilities towards the safety of subjects and the safety of a product under clinical investigation are met.

GSK has a legal responsibility to notify both the local regulatory authority and other regulatory agencies about the safety of a product under clinical investigation. GSK will comply with country specific regulatory requirements relating to safety reporting to the regulatory authority, Institutional Review Board (IRB)/Independent Ethics Committee (IEC) and investigators.

Investigator safety reports are prepared for suspected unexpected serious adverse reactions according to local regulatory requirements and GSK policy and are forwarded to investigators as necessary.

An investigator who receives an investigator safety report describing a SAE(s) or other specific safety information (e.g., summary or listing of SAEs) from GSK will file it with the IB and will notify the IRB/IEC, if appropriate according to local requirements.

7.4.2. Pregnancy

- If a subject becomes pregnant during the study they should discontinue Investigational Product.
- Any pregnancy that occurs during study participation (i.e., from baseline/randomization through the end of the post-treatment follow-up period) must be reported using a clinical trial pregnancy form.

If a pregnancy is reported then the investigator should inform GSK within 2 weeks of learning of the pregnancy and should follow the procedures outlined in [Appendix 6](#).

7.4.3. Physical Exams

A full or brief physical examination will be performed at the time points specified in the Time and Events Table Section [7.1](#)

- A full physical examination will include, at a minimum, assessment of the skin (including injection site), head, eyes, ears, nose, throat, thyroid, respiratory system cardiovascular system, abdomen (liver and spleen), lymph nodes, central nervous system and extremities.
- Brief physical examination includes evaluation of skin (including injection site), respiratory system, cardiovascular system, abdomen (liver, spleen), and central nervous system
- Investigators should pay special attention to clinical signs related to previous serious illnesses
- Height will be measured and recorded at screening only. Height should be measured with the subject in indoor daytime clothing with no shoes.

Weight will be measured at the time points specified in the Time and Events Table Section [7.1](#)

Body mass index will be calculated at screening only.

7.4.4. Vital Signs

For vital signs (blood pressure and pulse rate), a single measurement will be taken at each clinic visit (Section 7.1). During visits when ECGs are scheduled, vital sign measurements will be taken after the completion of the ECG sampling. Subjects may be either in a semi-recumbent or seated position. During visits when ECGs are not scheduled, vital sign measurements will be taken while subjects are in a seated position after at least a 5-minute rest period. During visits where a blood draw is required, vital sign measurements will be taken prior to sample collection.

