7.4.5. Electrocardiogram (ECG)

- A single 12-lead ECG recording (with subject in semirecumbent position for 10 to 15 minutes before obtaining the ECG) will be performed at the time points specified in the Time and Events Table (Section 7.1) using an ECG machine that automatically calculates the heart rate and measures PR, QRS, QT, and QTc intervals. Refer to Section 5.5.5 for QTc withdrawal criteria.

All ECGs will be performed **before** measurement of vital signs and collection of blood samples for laboratory testing.

Investigators must compare the baseline ECG with the Visit 1 (screening) ECG. Any changes indicative of a new MI or unstable cardiovascular condition (i.e., life-threatening arrhythmia) should prompt the investigator to **not administer the investigational product** but rather to evaluate and treat the subject per local standard of care. If subsequent evaluation reveals that a new MI has occurred or unstable/accelerated angina is documented, then the subject will not be included in the study. If subsequent evaluation reveals no evidence of ischemic damage or instability, then study treatment may proceed. If any screening ECG demonstrates a possible old MI that was unknown to the investigator and the subject, the subject should be evaluated and treated, as appropriate.

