8.2.10. Other Safety Measures

8.2.10.1. Vital Signs

The vital sign summary and analysis will include systolic blood pressure (mmHg), diastolic blood pressure (mmHg), and heart rate (bpm).

Each vital sign parameter at every scheduled assessment time point will be summarized using descriptive statistics and presented graphically. Change from Baseline will also be summarized using descriptive statistics and presented graphically. Additionally, the number of subjects with vital signs of potential clinical concern will also be summarized. Shift tables providing the number and percentage of subjects with indicated shifts (normal, low value of clinical concern, high value of clinical concern) in their results from baseline to each scheduled postbaseline assessment will also be presented. The criteria for vital signs of potential clinical concern are detailed in [Appendix 7: Values of Potential Clinical Importance](#).

All summaries will be done for the safety population and all vital sign data will be listed.

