11.3. Appendix 3: Assessment Windows

11.3.1. Definitions of Baseline and Study Day

In general, the baseline value for each variable will be defined as the last measurement collected prior to the first dose of randomized study medication.

Study day will be defined as the number of days from the first dose of randomized study medication. The date when a subject receives the first dose of randomized study medication is defined as Day 1. For events after the first dose date, study day is calculated as the difference in days between the first dose date and the date of interest, plus 1 day. For events that occur before the first dose date, study day is calculated as the difference in days between the first dose date and the date of interest. Thus, the day before first dose date is defined as Day -1.

Note that the date of first dose is Day 1 and the day before the date of first dose is Day -1 (there is no Day 0).

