11.3.4. Analysis Visit Windows

For vital sign assessments (except weight):

Scheduled Visit	Target Study Day of Visit	Slotting Intervals
Pre-therapy		
Screening (Week -2)	-14	Not applicable
Baseline (Week 0)	1	Not applicable
On-therapy		
Week 1	8	2 to 11 days
Week 2	15	12 to 18 days
Week 3	22	19 to 25 days
Week 4	29	26 to 32 days
Week 5	36	33 to 39 days
Week 6	43	40 to 46 days
Week 7	50	47 to 53 days
Week 8	57	54 to 60 days
Week 9	64	61 to 67 days
Week 10	71	68 to 74 days
Week 11	78	75 to 81 days
Week 12	85	82 to 92 days
Week 14	99	93 to 106 days
Week 16	113	107 to 120 days
Week 18	127	121 to 134 days

Scheduled Visit	Target Study Day of Visit	Slotting Intervals
Week 20	141	135 to 148 days
Week 22	155	149 to 165 days
Week 25	176	166 to 179 days
Week 26 (End of Treatment Visit)*	183	180 to (last dose date + 25 days)
Post-therapy		
Week 34**	239	>Last dose date + 25 days
8 Week Follow-up Visit**	Last dose date + 63 days***	>Last dose date + 25 days

* Week 26 is the end of treatment visit for those subjects completing the study per-protocol. For subjects who withdraw early from study treatment, the end of treatment visit will be assigned to an analysis visit based on the visit slotting algorithm using study day and therapy phase.
 
** Week 34 is the 8 week post-treatment follow-up visit for those subjects completing the study per-protocol. The 8 Week Follow-up Visit is the 8 week post-treatment follow-up visit for those subjects who withdraw early from study treatment. Both visits will be assigned based on the visit slotting algorithm using therapy phase.
 
*** The target study day for the 8 Week Follow-up Visit for subjects who withdraw early from study treatment is set to be 9 weeks (63 days) after last dose to correspond with the timing of the 8 week post-treatment follow-up for subjects completing the study per-protocol (where last dose is at Week 25 and the follow-up visit is at Week 34).
		

For ECG assessments:

Scheduled Visit	Target Study Day of Visit	Slotting Intervals
Pre-therapy		
Week -2	-14	Not applicable
Baseline (Week 0)	1	Not applicable
On-therapy		
Week 2	15	2 to 22 days
Week 4	29	23 to 43 days
Week 8	57	44 to 120 days
Week 26 (End of Treatment Visit)*	183	121 to (last dose date + 25 days)
Post-therapy		
Week 34**	239	>Last dose date + 25 days
8 Week Follow-up Visit**	Last dose date + 63 days***	>Last dose date + 25 days

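### Vital signs may be taken semi-recumbent or seated at ECG visits, including baseline, but only seated elsewhere, so change from baseline can mix posture with true change

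*Protocol*

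**What the plan says.** Protocol 7.4.4 asks for a single blood pressure and pulse measurement per visit, under a rule that depends on whether an ECG is due.

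- **ECG visits:** "During visits when ECGs are scheduled, vital sign measurements will be taken after the completion of the ECG sampling". The next sentence gives the posture: "Subjects may be either in a semi-recumbent or seated position". It names no rest period for a subject who is moved to a chair.
- **Other visits:** "vital sign measurements will be taken while subjects are in a seated position after at least a 5-minute rest period".

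Protocol 7.4.5 has the ECG recorded "with subject in semirecumbent position for 10 to 15 minutes before obtaining the ECG", so at ECG visits the subject has just been semi-recumbent when vital signs fall due.

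Baseline comes under the first rule. SAP 11.3.1 says "the baseline value for each variable will be defined as the last measurement collected prior to the first dose of randomized study medication", which is normally Week 0. Protocol 7.4.5 confirms an ECG both there and at screening: "Investigators must compare the baseline ECG with the Visit 1 (screening) ECG". If Week 0 is missing and screening is used instead, that is also an ECG visit.

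SAP 8.2.10.1 summarises each vital sign by visit and adds: "Change from Baseline will also be summarized using descriptive statistics and presented graphically". It also plans shift tables and counts of values of potential concern. SAP 11.7.2 flags an increase or decrease of more than 30 mmHg or 30 bpm from baseline. None of these sections mentions position. By contrast, SAP 11.7.3 labels its ECG heart-rate limits as supine.

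**The concern.** A change from baseline is meant to isolate what happened after treatment began. Here the two values being subtracted may, by rule, come from different postures. Posture can affect blood pressure and heart rate, and neither document says that it is recorded, held constant within a subject or adjusted for. As written, an analyst could not separate the two afterwards.

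Vital signs are a named secondary safety endpoint and are reported descriptively, so a reader will rely on the by-visit curves and flag counts. If many subjects were semi-recumbent at baseline, part of the plotted change at the seated visits would be an artefact of how the measurement was taken.

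**Working it through.** The plan states no figure on this point, so there is nothing to reproduce. The check has three parts.

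**1. How many visits are exposed.** The inputs are the visit-window tables in SAP 11.3.4. They are used because the columns of Protocol Table 4 are displaced in the text available for review.

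- On-therapy vital-sign visits: Weeks 1 to 12, 14, 16, 18, 20, 22, 25 and 26, which is 12 + 7 = 19.
- On-therapy ECG visits: Weeks 2, 4, 8 and 26, which is 4.
- Seated-only visits: 19 − 4 = 15, and 15/19 = 79%.

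If 7.4.4 is read literally, with vital signs at every weekly visit, the count is 26 − 4 = 22 of 26 (85%). The four ECG visits are not immune either, because a subject may choose a different posture there from the one at baseline.

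**2. Size within an arm.** Three inputs are assumptions, because the documents give none of them: the share f semi-recumbent at baseline, the posture difference d, and the SD of change.

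The shift in mean change at a seated visit is f × d:

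| f | d = 2 | d = 5 | d = 8 |
|---|---|---|---|
| 0 | 0 | 0 | 0 |
| 0.25 | 0.5 | 1.25 | 2.0 |
| 0.5 | 1.0 | 2.5 | 4.0 |
| 1 | 2 | 5 | 8 |

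For the flags, take a Normal change with SD 14 and mean d in subjects semi-recumbent at baseline, and mean 0 in the rest. Then P(d) = P(change > 30) + P(change < −30), and the share flagged is (1 − f) × P(0) + f × P(d).

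- P(0) = 3.2%, P(2) = 3.4%, P(4) = 3.9%, P(8) = 6.1%.
- With d = 8 and f = 0.25: 0.75 × 3.2% + 0.25 × 6.1% = 3.9%.
- With d = 8 and f = 0.5: 0.5 × 3.2% + 0.5 × 6.1% = 4.7%.
- With d = 8 and f = 1: 6.1%.
- With f = 0 and any d: 3.2%.

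In an arm of 150, the values 3.2%, 4.7% and 6.1% are about 5, 7 and 9 subjects flagged at a visit. One d and one SD stand in here for systolic pressure, diastolic pressure and heart rate, so this is an illustration and not a forecast for any one of them.

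**3. Size between arms.** With the same rule in both arms, the expected contribution to the liquid-minus-lyophilized difference is 0. Chance imbalance in f has a standard error of d × √(f(1 − f) × 2/150). At f = 0.5 this is 0.12, 0.29 and 0.46 for d = 2, 5 and 8.

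**The case against.** The best reply is that 7.4.4 gives a permission and does not describe what happens. A site that seats everyone at ECG visits complies fully and has essentially no mismatch. This stands. It is why the range above starts at no effect, and why 6.1% is only a ceiling: it needs every subject to be semi-recumbent at baseline.

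Protocol 7.4 refers to the Study Reference Manual for detailed procedures, and the eCRF might record position. Neither document is available here, so posture may be controlled better in practice than the protocol shows. But the protocol itself expressly offers the choice, and a manual that narrows it should not be presumed.

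The comparison of interest is randomised, double-blind and double-dummy, with the same rule in both arms, and Protocol 9.4.2 excludes inferential testing of safety variables. This stands in full. Part of the safety picture is also protected. Heart rate from the ECG is recorded semi-recumbent at baseline and at Weeks 2, 4, 8 and 26, with its own change-from-baseline summary. Limits on absolute values do not subtract baseline, and the shift tables compare categories of concern.

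A reader might infer two stronger things. One is that the curves will show a posture step at seated visits that vanishes at Weeks 2, 4, 8 and 26. That would need most subjects to be semi-recumbent at baseline and again at those four visits, and nothing in the documents shows this. The other is that one product is favoured, which a common rule under randomisation and blinding gives no reason to expect.

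**Conclusion.** The point holds as a minor weakness in measurement. The protocol's own rule lets baseline and follow-up values come from different postures at 15 of 19 on-therapy visits, and the SAP subtracts one from the other without regard to position.

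The consequence is limited to within-arm descriptive changes and the flags for changes over 30, with some added noise in the comparison of products. The size cannot be fixed from the documents. Under the stated assumptions it runs from nothing to about 3 percentage points more subjects flagged (6.1% − 3.2% = 2.9 points). The zero end also assumes that the missing rest period for subjects seated after an ECG makes no difference. The primary HbA1c analysis and its non-inferiority conclusion are not touched.

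**What to change.** In Protocol 7.4.4, replace the choice of posture at ECG visits with the rule already used elsewhere: after the ECG, seat the subject for at least 5 minutes and measure seated. Every by-visit change is then seated against seated, and the SAP needs no change.

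The cost is one sentence and about 5 minutes at each of the six scheduled ECG visits (screening and Weeks 0, 2, 4, 8 and 26), plus the Week 34 ECG that Table 5 adds for subjects who discontinue product.

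The change belongs before enrolment, since a switch part-way would create a before-and-after posture difference of its own. If it can only be made later, record position on the eCRF at each measurement, so that same-posture changes can be summarised separately.

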7.4.5. Electrocardiogram (ECG)

- A single 12-lead ECG recording (with subject in semirecumbent position for 10 to 15 minutes before obtaining the ECG) will be performed at the time points specified in the Time and Events Table (Section 7.1) using an ECG machine that automatically calculates the heart rate and measures PR, QRS, QT, and QTc intervals. Refer to Section 5.5.5 for QTc withdrawal criteria.

All ECGs will be performed **before** measurement of vital signs and collection of blood samples for laboratory testing.

Investigators must compare the baseline ECG with the Visit 1 (screening) ECG. Any changes indicative of a new MI or unstable cardiovascular condition (i.e., life-threatening arrhythmia) should prompt the investigator to **not administer the investigational product** but rather to evaluate and treat the subject per local standard of care. If subsequent evaluation reveals that a new MI has occurred or unstable/accelerated angina is documented, then the subject will not be included in the study. If subsequent evaluation reveals no evidence of ischemic damage or instability, then study treatment may proceed. If any screening ECG demonstrates a possible old MI that was unknown to the investigator and the subject, the subject should be evaluated and treated, as appropriate.

7.4.6. Clinical Safety Laboratory Assessments

All protocol required laboratory assessments, as defined in Table 6 must be conducted in accordance with the Laboratory Manual, and Protocol Time and Events Schedule in Section 7.1. Laboratory requisition forms must be completed and samples must be clearly labeled with the subject number, protocol number, site/centre number, and visit date. Details for the preparation and shipment of samples will be provided by the laboratory and are detailed in the laboratory manual. Reference ranges for all safety parameters will be provided to the site by the laboratory responsible for the assessments.

If additional non-protocol specified laboratory assessments are performed at the institution's local laboratory and result in a change in subject management or are considered clinically significant by the investigator (e.g., SAE or AE or dose modification) the results must be recorded in the eCRF.

Refer to the SRM for appropriate processing and handling of samples to avoid duplicate and/or additional blood draws.

All study-required laboratory assessments will be performed by a central laboratory, apart from HbA_{1c} at screening where a local or central laboratory may be used. HbA_{1c} results from a local laboratory must be entered into the eCRF.

Hematology, clinical chemistry, urinalysis and additional parameters to be tested are listed in [Table 6](#).

Table 6 Protocol Required Safety Laboratory Assessments

Laboratory Assessments	Parameters			
Hematology	Platelet Count	Red blood cell (RBC) Indices:		White blood cell (WBC) count with Differential:
	RBC Count	mean corpuscular volume (MCV)		Neutrophils
	Hemoglobin	mean corpuscular hemoglobin (MCH)		Lymphocytes
	Hematocrit			Monocytes
				Eosinophils
				Basophils
Clinical Chemistry ¹	Blood urea nitrogen (BUN)	Potassium	Aspartate amino transferase (AST (SGOT))	Total and direct bilirubin
	Creatinine	Sodium	ALT (SGPT)	Total Protein
	Calcium	chloride	Alkaline phosphatase	Albumin
	bicarbonate	Uric acid	Gamma glutamyl transferase (GGT)	
Routine Urinalysis	
 • Specific gravity • pH, glucose, protein, blood and ketones by dipstick • Microscopic examination (if blood or protein is abnormal) 			
Other Laboratory Tests	
 • HbA_{1c} • FPG • Amylase^{2,5} • Lipase^{2,5} • HIV² • TSH^{2,3} • Lipids including total cholesterol, LDL-C, HDL C, triglycerides, FFAs (fasting)⁴ • Hepatitis B (HBsAg)² • Hepatitis C (Hep C antibody)² • FSH and estradiol (as needed in women of non-child bearing potential only) • Alcohol and drug screen (to include at minimum: amphetamines, barbiturates, cocaine, opiates, cannabinoids and benzodiazepines)² • Serum or urine hCG Pregnancy test (as needed for women of child bearing potential) 			

 1. Details of Liver Chemistry Stopping Criteria and Required Actions and Follow-Up Assessments after liver stopping or monitoring event are given in Section 5.5.4 and Appendix 3. 2. Measured at screening only. 3. Free T4 (reflex) will be measured if TSH is above the upper limit of normal 4. Fasting is defined as no food or drink (except water) for at least 8 hours before blood draw 5. Samples will be stored for calcitonin measurement in the event of MTC related events. 				

All laboratory tests with values that are considered clinically significantly abnormal during participation in the study or within 25 days after the last dose of study treatment should be repeated until the values return to normal or baseline. If such values do not return to normal within a period judged reasonable by the investigator, the etiology should be identified and the sponsor notified.

